8.3.1. Time Period and Frequency for Collecting AE and SAE Information

The time period for actively eliciting and collecting AEs and SAEs (“active collection period”) for each participant begins from the time the participant provides informed consent, which is obtained before the participant’s participation in the study (ie, before undergoing any study-related procedure and/or receiving study intervention), through and including a minimum of 28 calendar days, except as indicated below, after the last administration of the study intervention.

Follow-up by the investigator continues throughout and after the active collection period and until the AE or SAE or its sequelae resolve or stabilize at a level acceptable to the investigator.

For participants who are screen failures, the active collection period ends when screen failure status is determined.

If the participant withdraws from the study and also withdraws consent for the collection of future information, the active collection period ends when consent is withdrawn.

If a participant permanently discontinues or temporarily discontinues study intervention because of an AE or SAE, the AE or SAE must be recorded on the CRF and the SAE reported using the CT SAE Report Form.

Investigators are not obligated to actively seek information on AEs or SAEs after the participant has concluded study participation. However, if the investigator learns of any SAE, including a death, at any time after a participant has completed the study, and he/she considers the event to be reasonably related to the study intervention, the investigator must promptly report the SAE to Pfizer using the CT SAE Report Form.

8.3.1.1. Reporting SAEs to Pfizer Safety

All SAEs occurring in a participant during the active collection period as described in Section 8.3.1 are reported to Pfizer Safety on the CT SAE Report Form immediately upon awareness and under no circumstance should this exceed 24 hours, as indicated in

Appendix 3. The investigator will submit any updated SAE data to the sponsor within 24 hours of it being available.

8.3.1.2. Recording Nonserious AEs and SAEs on the CRF

All nonserious AEs and SAEs occurring in a participant during the active collection period, which begins after obtaining informed consent as described in [Section 8.3.1](#), will be recorded on the AE section of the CRF.

The investigator is to record on the CRF all directly observed and all spontaneously reported AEs and SAEs reported by the participant.

8.3.2. Method of Detecting AEs and SAEs

The method of recording, evaluating, and assessing causality of AEs and SAEs and the procedures for completing and transmitting SAE reports are provided in [Appendix 3](#).

Care will be taken not to introduce bias when detecting AEs and/or SAEs. Open-ended and nonleading verbal questioning of the participant is the preferred method to inquire about AE occurrences.

8.3.3. Follow-Up of AEs and SAEs

After the initial AE or SAE report, the investigator is required to proactively follow each participant at subsequent visits/contacts. For each event, the investigator must pursue and obtain adequate information until resolution, stabilization, the event is otherwise explained, or the participant is lost to follow-up (as defined in [Section 7.3](#)).

In general, follow-up information will include a description of the event in sufficient detail to allow for a complete medical assessment of the case and independent determination of possible causality. Any information relevant to the event, such as concomitant medications and illnesses, must be provided. In the case of a participant death, a summary of available autopsy findings must be submitted as soon as possible to Pfizer Safety.

Further information on follow-up procedures is given in [Appendix 3](#).

8.3.4. Regulatory Reporting Requirements for SAEs

Prompt notification by the investigator to the sponsor of an SAE is essential so that legal obligations and ethical responsibilities toward the safety of participants and the safety of a study intervention under clinical investigation are met.

The sponsor has a legal responsibility to notify both the local regulatory authority and other regulatory agencies about the safety of a study intervention under clinical investigation. The sponsor will comply with country-specific regulatory requirements relating to safety reporting to the regulatory authority, IRBs/ECs, and investigators.

Investigator safety reports must be prepared for SUSARs according to local regulatory requirements and sponsor policy and forwarded to investigators as necessary.

An investigator who receives SUSARs or other specific safety information (eg, summary or listing of SAEs) from the sponsor will review and then file it along with the SRSD(s) for the study and will notify the IRB/EC, if appropriate according to local requirements.

8.3.5. Environmental Exposure, Exposure During Pregnancy or Breastfeeding, and Occupational Exposure

Environmental exposure occurs when a person not enrolled in the study as a participant receives unplanned direct contact with or exposure to the study intervention. Such exposure may or may not lead to the occurrence of an AE or SAE. Persons at risk for environmental exposure include healthcare providers, family members, and others who may be exposed. An environmental exposure may include exposure during pregnancy, exposure during breastfeeding, and occupational exposure.

Any such exposure to the study intervention under study are reportable to Pfizer Safety within 24 hours of investigator awareness.

8.3.5.1. Exposure During Pregnancy

An EDP occurs if:

- A female participant is found to be pregnant while receiving or after discontinuing study intervention.
- A male participant who is receiving or has discontinued study intervention exposes a female partner prior to or around the time of conception.
- A female is found to be pregnant while being exposed or having been exposed to study intervention due to environmental exposure. Below are examples of environmental EDP:
 - A female family member or healthcare provider reports that she is pregnant after having been exposed to the study intervention by ingestion, inhalation, or skin contact.
 - A male family member or healthcare provider who has been exposed to the study intervention by ingestion, inhalation, or skin contact then exposes his female partner prior to or around the time of conception.

The investigator must report EDP to Pfizer Safety within 24 hours of the investigator's awareness, irrespective of whether an SAE has occurred. The initial information submitted

should include the anticipated date of delivery (see below for information related to termination of pregnancy).

- If EDP occurs in a participant or a participant's partner, the investigator must report this information to Pfizer Safety on the CT SAE Report Form and an EDP Supplemental Form, regardless of whether an SAE has occurred. Details of the pregnancy will be collected after the start of study intervention and until 28 days after the last dose.
- If EDP occurs in the setting of environmental exposure, the investigator must report information to Pfizer Safety using the CT SAE Report Form and EDP Supplemental Form. Since the exposure information does not pertain to the participant enrolled in the study, the information is not recorded on a CRF; however, a copy of the completed CT SAE Report Form is maintained in the investigator site file.

Follow-up is conducted to obtain general information on the pregnancy and its outcome for all EDP reports with an unknown outcome. The investigator will follow the pregnancy until completion (or until pregnancy termination) and notify Pfizer Safety of the outcome as a follow-up to the initial EDP Supplemental Form. In the case of a live birth, the structural integrity of the neonate can be assessed at the time of birth. In the event of a termination, the reason(s) for termination should be specified and, if clinically possible, the structural integrity of the terminated fetus should be assessed by gross visual inspection (unless preprocedure test findings are conclusive for a congenital anomaly and the findings are reported).

Abnormal pregnancy outcomes are considered SAEs. If the outcome of the pregnancy meets the criteria for an SAE (ie, ectopic pregnancy, spontaneous abortion, intrauterine fetal demise, neonatal death, or congenital anomaly in a live-born baby, a terminated fetus, an intrauterine fetal demise, or a neonatal death), the investigator should follow the procedures for reporting SAEs. Additional information about pregnancy outcomes that are reported to Pfizer Safety as SAEs follows:

- Spontaneous abortion including miscarriage and missed abortion;
- Neonatal deaths that occur within 1 month of birth should be reported, without regard to causality, as SAEs. In addition, infant deaths after 1 month should be reported as SAEs when the investigator assesses the infant death as related or possibly related to exposure to the study intervention.

Additional information regarding the EDP may be requested by the sponsor. Further follow-up of birth outcomes will be handled on a case-by-case basis (eg, follow-up on preterm infants to identify developmental delays). In the case of paternal exposure, the investigator will provide the participant with the Pregnant Partner Release of Information Form to deliver to his partner. The investigator must document in the source documents that the participant was given the Pregnant Partner Release of Information Form to provide to his partner.

8.3.5.2. Exposure During Breastfeeding

An exposure during breastfeeding occurs if:

- A female participant is found to be breastfeeding while receiving or after discontinuing study intervention.
- A female is found to be breastfeeding while being exposed or having been exposed to study intervention (ie, environmental exposure). An example of environmental exposure during breastfeeding is a female family member or healthcare provider who reports that she is breastfeeding after having been exposed to the study intervention by ingestion, inhalation, or skin contact.

The investigator must report exposure during breastfeeding to Pfizer Safety within 24 hours of the investigator's awareness, irrespective of whether an SAE has occurred. The information must be reported using the CT SAE Report Form. When exposure during breastfeeding occurs in the setting of environmental exposure, the exposure information does not pertain to the participant enrolled in the study, so the information is not recorded on a CRF. However, a copy of the completed CT SAE Report Form is maintained in the investigator site file.

An exposure during breastfeeding report is not created when a Pfizer drug specifically approved for use in breastfeeding women (eg, vitamins) is administered in accord with authorized use. However, if the infant experiences an SAE associated with such a drug, the SAE is reported together with the exposure during breastfeeding.

8.3.5.3. Occupational Exposure

The investigator must report any instance of occupational exposure to Pfizer Safety within 24 hours of the investigator's awareness using the CT SAE Report Form regardless of whether there is an associated SAE. Since the information about the occupational exposure does not pertain to a participant enrolled in the study, the information is not recorded on a CRF; however, a copy of the completed CT SAE Report Form must be maintained in the investigator site file.

8.3.6. Cardiovascular and Death Events

Not applicable.

8.3.7. Disease-Related Events and/or Disease-Related Outcomes Not Qualifying as AEs or SAEs

Not applicable.

8.3.8. Adverse Events of Special Interest

Adverse events of special interest (AESIs) are examined as part of routine safety data review procedures throughout the clinical trial and as part of signal detection processes.

All AESIs must be reported as an AE or SAE following the procedures described in **Section 8.3.1** through **8.3.4**. An AESI is to be recorded as an AE or SAE on the CRF. In addition, an AESI that is also an SAE must be reported using the CT SAE Report Form.

8.3.8.1. Lack of Efficacy

This section is not applicable because efficacy is not expected in the study population.

8.3.9. Medical Device Deficiencies

Not applicable.

8.3.10. Medication Errors

Medication errors may result from the administration or consumption of the study intervention by the wrong participant, or at the wrong time, or at the wrong dosage strength.

Exposures to the study intervention under study may occur in clinical trial settings, such as medication errors.

Safety Event	Recorded on the CRF	Reported on the CT SAE Report Form to Pfizer Safety Within 24 Hours of Awareness
Medication errors	All (regardless of whether associated with an AE)	Only if associated with an SAE

Medication errors include:

- Medication errors involving participant exposure to the study intervention;
- Potential medication errors or uses outside of what is foreseen in the protocol that do or do not involve the study participant.

Such medication errors occurring to a study participant are to be captured on the medication error page of the CRF, which is a specific version of the AE page.

In the event of a medication dosing error, the sponsor should be notified within 24 hours.

Whether or not the medication error is accompanied by an AE, as determined by the investigator, the medication error is recorded on the medication error page of the CRF and, if applicable, any associated AE(s), serious and nonserious, are recorded on the AE page of the CRF.

Medication errors should be reported to Pfizer Safety within 24 hours on a CT SAE Report Form **only when associated with an SAE**.

8.4. Pharmacokinetics

8.4.1. Plasma for Analysis of PF-07321332 CCI

Blood samples of approximately 4 mL, to provide approximately 1.5 mL plasma, will be collected for measurement of plasma concentrations of PF-07321332 CCI as specified in the **SoA**. Instructions for the collection and handling of biological samples will be provided in the laboratory manual or by the sponsor. The actual date and time (24-hour clock time) of each sample will be recorded.

The actual times may change, but the number of samples will remain the same. All efforts will be made to obtain the samples at the exact nominal time relative to dosing. Collection of samples up to and including 10 hours after dose administration that are obtained within 10% of the nominal time relative to dosing (eg, within 6 minutes of a 60-minute sample) will not be captured as a protocol deviation, as long as the exact time of the collection is noted on the source document and the CRF. Collection of samples more than 10 hours after dose administration that are obtained \leq 1 hour away from the nominal time relative to dosing will not be captured as a protocol deviation, as long as the exact time of the collection is noted on the source document and the CRF.

Samples will be used to evaluate the PK of PF-07321332 CCI. Samples collected for analyses of PF-07321332 CCI concentration may also be used to evaluate safety or efficacy aspects related to concerns arising during or after the study, for metabolite identification, analysis of endogenous biomarkers, and/or evaluation of the bioanalytical method, CCI.

Genetic analyses will not be performed on these plasma samples unless consent for this was included in the informed consent. Participant confidentiality will be maintained.

Samples collected for measurement of plasma concentrations of PF-07321332 CCI will be analyzed using a validated analytical method in compliance with applicable SOPs. Potential metabolites may be analyzed with either validated CCI methods.

The PK samples must be processed and shipped as indicated in the instructions provided to the investigator site to maintain sample integrity. Any deviations from the PK sample handling procedure (eg, sample collection and processing steps, interim storage or shipping conditions), including any actions taken, must be documented and reported to the sponsor. On a case-by-case basis, the sponsor may make a determination as to whether sample integrity has been compromised.

Any changes in the timing or addition of time points for any planned study assessments must be documented and approved by the relevant study team member and then archived in the sponsor and site study files, but will not constitute a protocol amendment. The IRB/EC will be informed of any safety issues that require alteration of the safety monitoring scheme or amendment of the ICD.

8.5. Genetics

8.5.1. Specified Genetics

Genetics (specified analyses) are not evaluated in this study.

CCI

8.6. Biomarkers

Biomarkers are not evaluated in this study.

8.6.1. Specified Gene Expression (RNA) Research

Specified gene expression (RNA) research is not included in this study.

8.6.2. Specified Protein Research

Specified protein research is not included in this study.

8.6.3. Specified Metabolomic Research

Specified metabolomic research is not included in this study.

CCI

8.7. Immunogenicity Assessments

Immunogenicity assessments are not included in this study.

8.8. Health Economics

Health economics/medical resource utilization and health economics parameters are not evaluated in this study.

9. STATISTICAL CONSIDERATIONS

Detailed methodology for summary and statistical analyses of the data collected in this study is outlined here and further detailed in a SAP, which will be maintained by the sponsor. The SAP may modify what is outlined in the protocol where appropriate; however, any major modifications of the primary endpoint definitions or their analyses will also be reflected in a protocol amendment.

9.1. Statistical Hypotheses

There are no statistical hypotheses for this study.

9.2. Analysis Sets

For purposes of analysis, the following analysis sets are defined:

Participant Analysis Set	Description
Enrolled/Randomly assigned to study intervention	"Enrolled" means a participant's, or their legally authorized representative's, agreement to participate in a clinical study following completion of the informed consent process and screening. Potential participants who are screened for the purpose of determining eligibility for the study, but do not participate in the study, are not considered enrolled, unless otherwise specified by the protocol. A participant will be considered enrolled if the informed consent is not withdrawn prior to participating in any study activity after screening.
Safety Analysis Set	All participants who take at least 1 dose of study intervention. Participants will be analyzed according to the product they actually received.
PK Concentration Set	All participants who take at least 1 dose of study intervention and in whom at least 1 concentration value is reported.
PK Parameter Set	All participants who take at least 1 dose of study intervention and in whom at least 1 of the PK parameters of interest are reported.

9.3. Statistical Analyses

The SAP will be developed and finalized before any analyses are performed and will describe the analyses and procedures for accounting for missing, unused, and spurious data. This section is a summary of the planned statistical analyses of the primary and secondary endpoints.

9.3.1. Pharmacokinetic Analyses

9.3.1.1. Derivation of Pharmacokinetic Parameters

Plasma PK parameters of PF-07321332 CCI will be derived (as data permit) from the concentration-time data using standard noncompartmental methods as outlined in the Table below. Actual PK sampling times will be used in the derivation of PK parameters. In the case that actual PK sampling times are not available, nominal PK sampling time will be used in the derivation of PK parameters.

Plasma PF-07321332 CCI PK Parameters Definitions

Parameter	Definition	Method of Determination
AUC _{last}	Area under the plasma concentration-time profile from time zero to the time of the last quantifiable concentration (C _{last}).	Linear/Log trapezoidal method.
AUC _{tau}	Area under the plasma concentration-time profile from time zero to time tau (τ), where tau=12-hour dosing interval.	Linear/Log trapezoidal method.
C _{max}	Maximum observed concentration	Observed directly from data
T _{max}	Time for C _{max}	Observed directly from data as time of first occurrence
t _{1/2} *	Terminal half-life	Log _e (2)/k _{el} , where k _{el} is the terminal phase rate constant calculated by a linear regression of the loglinear concentration-time curve. Only those data points judged to describe the terminal loglinear decline will be used in the regression.
CL/F	Apparent clearance	Dose/AUC _{tau}
V _z /F*	Apparent volume of distribution	Dose/(AUC _{tau} • k _{el})

*If data permit.

9.3.2. Statistical Methods for PK Data

The plasma concentrations of PF-07321332 CCI will be listed and descriptively summarized by nominal PK sampling time and treatment. Individual participant, as well as mean and median profiles of the plasma concentration time data will be plotted by treatment for each analyte using actual (for individual) and nominal (for mean and median) times respectively. Mean and median profiles will be presented on both linear and semi-log scales. Box and whisker plots for AUC_{tau} and C_{max} following multiple doses of PF-07321332/ritonavir will be plotted by treatment.

Natural log transformed parameters (AUC_{tau}, and C_{max}) of PF-07321332 will be analyzed using a mixed effect model with treatment as fixed effect and participant as a random effect. Estimates of the adjusted mean differences (Test-Reference) and corresponding 90% CIs will be obtained from the model. The adjusted mean differences and 90% CIs for the differences will be exponentiated to provide estimates of the ratio of adjusted geometric means (Test/Reference) and 90% CI for the ratios. PF-07321332/ritonavir administered alone will be the Reference treatment and PF-07321332/ritonavir co-administered with itraconazole will be the Test treatment.

Additional specifications about the tables, listings, and figures will be outlined in the SAP.

9.3.3. Other Safety Analyses

All safety analyses will be performed on the safety population.

AEs, ECGs, BP, PR, and safety laboratory data will be reviewed and summarized on an ongoing basis during the study to evaluate the safety of participants. Any clinical laboratory, ECG, BP, and PR abnormalities of potential clinical concern will be described. Safety data will be presented in tabular and/or graphical format and summarized descriptively, where appropriate.

Medical history and PE and neurological examination information, as applicable, collected during the course of the study will be considered source data and will not be required to be reported, unless otherwise noted. However, any untoward findings identified on physical and/or neurological examinations conducted during the active collection period will be captured as AEs, if those findings meet the definition of an AE. Data collected at Screening that are used for inclusion/exclusion criteria, such as laboratory data, ECGs, and vital signs, will be considered source data, and will not be required to be reported, unless otherwise noted. Demographic data collected at Screening will be reported.

CCI

9.4. Interim Analyses

No formal interim analysis will be conducted for this study. As this is an open-label study, the sponsor may conduct unblinded reviews of the data during the course of the study for the purpose of safety assessment, facilitating PK/PD modeling, and/or supporting clinical development.

9.5. Sample Size Determination

A sample size of 9 participants will provide adequate precision to estimate the effects of itraconazole on the PK of PF-07321332. The expected widths of the 90% CIs with 80% coverage probability are shown in the following table for a range of possible effects.

Parameter	Estimated Effect (100*Test/Reference)	90% CI	CI Width
AUC _{tau}	100%	88%, 113%	25%
	110%	97%, 124%	27%
	120%	106%, 136%	30%
	130%	115%, 147%	32%
	140%	124%, 158%	35%
C _{max}	100%	92%, 108%	16%
	110%	102%, 119%	17%
	120%	111%, 130%	19%
	130%	120%, 141%	21%
	140%	129%, 152%	22%

These estimates are based on the assumption that within-participant standard deviations are 0.14 and 0.091 for lnAUC_{tau} and lnC_{max}, respectively, as obtained from ongoing clinical study C4671001 in healthy participants.

To allow for dropouts, 12 participants will be enrolled in order to have 9 PK evaluable participants. Participants who withdraw from the study may be replaced at the discretion of the investigator upon consultation with the sponsor.

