- Period 1: 300 mg PF-07321332/100 mg ritonavir administered orally, q12h for 5 doses: Day 1 morning to Day 3 morning.

- Period 2: 200 mg itraconazole, administered orally, QD, on Days 1 through 8, inclusive. On Days 4 through 6, participants will receive 300 mg PF-07321332/100 mg ritonavir administered orally, q12h for 5 doses: Day 4 morning to Day 6 morning.

Participants will be discharged on Period 2, Day 9 following completion of all assessments.

The total planned duration of participation, from the Screening visit to the last Follow-up phone call, is approximately 10 weeks.

Data Monitoring Committee or Other Independent Oversight Committee: No

Statistical Methods

Sample Size Determination

A sample size of 9 participants will provide adequate precision to estimate the effects of itraconazole on the PK of PF-07321332. The expected widths of the 90% CIs with 80% coverage probability are shown in the following table for a range of possible effects.

Parameter	Estimated Effect (100%*Test/Reference)	90% CI	CI Width
AUC _{tau}	100%	88%, 113%	25%
	110%	97%, 124%	27%
	120%	106%, 136%	30%
	130%	115%, 147%	32%
	140%	124%, 158%	35%
C _{max}	100%	92%, 108%	16%
	110%	102%, 119%	17%
	120%	111%, 130%	19%
	130%	120%, 141%	21%
	140%	129%, 152%	22%

These estimates are based on the assumption that within-participant standard deviations are 0.14 and 0.091 for lnAUC_{tau} and lnC_{max}, respectively, as obtained from ongoing clinical Study C4671001 in healthy participants.

To allow for dropouts, 12 participants will be enrolled in order to have 9 PK evaluable participants. Participants who withdraw from the study may be replaced at the discretion of the investigator upon consultation with the sponsor.

Pharmacokinetics Analysis

The PK concentration population is defined as all participants who take at least 1 dose of study intervention and in whom at least 1 concentration value is reported.

The PK parameter analysis population is defined as all participants who take at least 1 dose of study intervention and in whom at least 1 of the PK parameters of primary interest are reported.

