4. STUDY DESIGN

4.1. Overall Design

This is a Phase 1, open-label, 2-period, fixed-sequence crossover study to estimate the effect of the strong CYP3A4 inhibitor, itraconazole, on the PK of PF-07321332 in healthy participants. The study will consist of 2 treatments: multiple oral doses of 300 mg PF-07321332/100 mg ritonavir alone and multiple oral doses of 300 mg PF-07321332/100 mg ritonavir in combination with itraconazole. A total of approximately 12 healthy male and/or female participants will be enrolled into the study to ensure at least 9 participants will complete the study. The treatment will consist of a single-fixed sequence.

Participants who discontinue from the study for non-safety reasons may be replaced at the sponsor's discretion in collaboration with the Investigator.

Healthy participants will be screened to determine eligibility within 28 days prior to study treatment. Medical history and results of physical examination, physical measurements, vital signs, 12-lead ECGs, and clinical laboratory evaluations will determine eligibility.

Participants will report to the CRU on Day -1, at least 12 hours prior to Day 1 dosing in Period 1 and will be required to stay in the CRU for 14 days and 13 nights.

In Period 1, each enrolled participant will receive 300 mg PF-07321332/100 mg ritonavir administered orally, q12h for 5 doses, from Day 1 morning to Day 3 morning. Serial PK samples will be collected up to 48 hours post the 5th dose on Day 3 to establish baseline exposure of PF-07321332 and ritonavir. PK samples will also be collected predose the morning and evening doses of PF-07321332/ritonavir on Day 2 to confirm steady state.

Period 2 will begin on Study Day 5 (referred to as Period 2, Day 1). Participants will receive 200 mg itraconazole, administered orally, QD on Period 2, Days 1 through 8, inclusive. On Days 4, 5, and 6, participants will receive 300 mg PF-07321332/100 mg ritonavir administered orally, q12h for 5 doses, from Day 4 morning to Day 6 morning. Following the final administration of PF-07321332/ritonavir on the morning of Day 6, participants will undergo serial PK sampling up to 72 hours post the last dose. PK samples will also be collected predose the morning and evening doses of PF-07321332/ritonavir on Day 5 to confirm steady state. Participants will be discharged from the CRU on Day 9 (Study Day 13) following completion of all assessments.

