8. STATISTICAL METHODOLOGY AND STATISTICAL ANALYSES

8.1. Statistical Methods

The interactive effect on PK parameters will be determined by constructing 90% confidence intervals around the estimated difference between the Test and Reference treatments using a mixed effects model based on natural log transformed data. The mixed effects model will be implemented using SAS Proc Mixed, with REML estimation method and Kenward-Roger degrees of freedom algorithm.

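### The 90% CI widths tabulated for 9 participants carry about a 57% chance under the planned paired analysis, not the stated 80%

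*Protocol*

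**What the plan says.** Protocol section 9.5 and the synopsis carry the same sample size argument. It opens with the claim "A sample size of 9 participants will provide adequate precision to estimate the effects of itraconazole on the PK of PF-07321332" and continues: "The expected widths of the 90% CIs with 80% coverage probability are shown in the following table for a range of possible effects". The table gives limits and widths at Test/Reference ratios of 100% to 140%. At 100% these are 88–113% (width 25) for AUCtau and 92–108% (width 16) for Cmax. The stated inputs are that "within-participant standard deviations are 0.14 and 0.091 for lnAUC_{tau} and lnC_{max}, respectively", taken from study C4671001. The enrolment figure is a dropout allowance: "12 participants will be enrolled in order to have 9 PK evaluable participants".

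On design and analysis, Protocol section 4.1 describes a two-period study in which every participant takes Reference and then Test. Protocol section 9.3.2 and SAP section 8.2 specify a model for the log parameters with treatment fixed and participant random. SAP section 8.1 adds that it is fitted "with REML estimation method and Kenward-Roger degrees of freedom algorithm". Neither document gives the formula behind the table, its degrees of freedom, or a definition of the 80% coverage probability.

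**The concern.** A probability attached to an interval width is an assurance statement: the observed interval should be no wider than tabulated in 80% of studies. The observed SD varies from study to study, so the tabulated half-width would have to include a margin for that variation. The printed limits look like ordinary t intervals computed at the assumed SD, which have no such margin and are met only a little more often than not.

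The study has no hypothesis and no decision rule (SAP sections 4.1 and 4.2), so stated precision is the whole case for 9 participants. If the 80% is wrong, the table overstates the chance of intervals this narrow and understates the width that carries 80% assurance, for both primary parameters.

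**Working it through.** **Inputs.** n = 9 evaluable; within-participant SD 0.14 (lnAUCtau) and 0.091 (lnCmax), from Protocol 9.5; two-sided 90% interval, treatment fixed, participant random, Kenward-Roger df, from SAP 8.1 and 8.2. With complete pairs this model gives the paired t interval on n − 1 df, so 8 df at n = 9.

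**Step 1: reproduce the table.** Log half-width with the SD at its assumed value: h = t(0.95, 8) × SD × √(2/9), with t(0.95, 8) = 1.8595.

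- AUCtau: 1.8595 × 0.14 × 0.4714 = 0.1227, giving 88.45–113.06% at ratio 100%.
- Cmax: 1.8595 × 0.091 × 0.4714 = 0.0798, giving 92.33–108.30%.

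Over all rows this matches 20 of 20 printed limits and 8 of 10 printed widths. The two misses are within one point: AUCtau at 140% (34.45, printed 35) and Cmax at 110% (17.57, printed 17).

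**Step 2: add the 80% allowance.** The half-width met with 80% probability is h × √(χ²(0.80, 8)/8) = h × √(11.030/8) = 1.174 h, that is 0.1441 (AUCtau) and 0.0937 (Cmax). This matches 0 of 20 printed limits.

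| Ratio | AUCtau printed | AUCtau, 80% assurance | Cmax printed | Cmax, 80% assurance |
|---|---|---|---|---|
| 100% | 88–113 (25) | 86.6–115.5 (28.9) | 92–108 (16) | 91.1–109.8 (18.8) |
| 110% | 97–124 (27) | 95.2–127.1 (31.8) | 102–119 (17) | 100.2–120.8 (20.6) |
| 120% | 106–136 (30) | 103.9–138.6 (34.7) | 111–130 (19) | 109.3–131.8 (22.5) |
| 130% | 115–147 (32) | 112.6–150.2 (37.6) | 120–141 (21) | 118.4–142.8 (24.4) |
| 140% | 124–158 (35) | 121.2–161.7 (40.5) | 129–152 (22) | 127.5–153.7 (26.3) |

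Widths in percentage points are in brackets.

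**Step 3: the chance actually attached to the table.** For n evaluable participants, the probability that the observed log half-width does not exceed the n = 9 value from step 1 is

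P(χ²(n−1) ≤ (n−1) × [t(0.95, 8)√(2/9) / (t(0.95, n−1)√(2/n))]²).

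The SD cancels, so the result is the same for both parameters.

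| n evaluable | t(0.95, n−1) | χ² bound | Probability |
|---|---|---|---|
| 9 | 1.8595 | 8.00 | 56.7% |
| 10 | 1.8331 | 10.29 | 67.3% |
| 11 | 1.8125 | 12.87 | 76.9% |
| 12 | 1.7959 | 15.72 | 84.8% |

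Simulation of 400,000 paired data sets per n gave 0.57, 0.67, 0.77 and 0.85.

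**Step 4: does the unknown formula or the rounding matter?** Any common multiplier (half-width ÷ SD) that rounds to all 20 printed limits lies between 0.8726 and 0.8838; step 1 gives 0.8766. Over that range the probability is 55.9% to 57.9% at n = 9, 76.2% to 78.1% at n = 11 and 84.3% to 85.8% at n = 12.

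**Step 5: reading the widths as averages.** The mean half-width at n = 9 is 0.969 of the step 1 value (AUCtau 0.119). The tabulated widths are therefore slightly above the mean, and the 80% describes neither reading.

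**The case against.** The strongest counter-argument is that the sponsor may well have applied an 80% factor. The formula 1.645 × SD × √(2/9) × √(χ²(0.80, d)/d) also gives all 20 printed limits for d = 14 to 17. At d = 16, which is 2(n − 1), it cannot be told apart from step 1, and at d = 15 it matches 9 of 10 printed widths against 8 of 10. That may be how the label arose, so the documents do not show that the allowance was simply left out. This part stands. It does not rescue the 80%: those df do not belong to 9 pairs, the planned interval does not use a normal quantile, and the same formula on 8 df matches only 10 of 20 limits. Step 4 shows that the origin of the table is immaterial to the probability.

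The term is also undefined, and the assurance reading is an interpretation. It is the natural one, and the average-width reading does not support 80% either.

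Twelve participants are to be enrolled, and those who withdraw may be replaced. If all 12 are evaluable, the chance is 85%. That mitigates the problem, but the claim is made for 9, and the extra three are there to cover dropouts.

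Finally, the consequence is small. Limits move by roughly 1 to 4 points, the documents set no width that must be achieved, and the reported intervals will use the observed variance. All of this stands. It limits the matter to the stated justification and does not show that 9 participants are too few.

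**Conclusion.** The 80% label is wrong as written, in both places. Under the planned analysis, 9 evaluable participants give about a 57% chance of intervals as narrow as tabulated. Twelve evaluable, not merely enrolled, is the smallest number that reaches 80%. At n = 9, intervals with genuine 80% assurance are about 17% wider on the log scale.

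This rests on three conditions: complete pairs analysed on n − 1 df, the 80% read as the probability that the width is not exceeded, and true SDs equal to 0.14 and 0.091. The documents do not say how precisely those SDs were estimated, and larger true values would lower the chances further. The analysis itself is not biased and no decision depends on the table. The correction should be made because this is the only quantitative argument for the sample size.

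**What to change.** Make one of two changes, identically in Protocol 9.5 and the synopsis.

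1. Keep the 80% statement and replace the limits and widths with the 80%-assurance columns of the step 2 table.
2. Keep the printed table, remove the reference to 80% coverage probability, and say that the limits apply if the observed SD equals the assumed SD, with about a 57% chance of being met with 9 evaluable participants and about 85% if all 12 are evaluable.

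In either case state the formula and degrees of freedom, and say what any quoted probability refers to. If the sponsor used a different planning formula, naming it would settle where the label came from, but the probability should still be the one that applies to the planned analysis.

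The cost is a text or table correction in two places and a slightly less favourable stated precision. Enrolment, conduct and analysis do not change.
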